10.8. Appendix 8: France Contrat Unique

1. GCP Training

Before enrolling any participants, the investigator and any sub investigators will complete the Pfizer provided Good Clinical Practice training course (“Pfizer GCP Training”) or training deemed equivalent by Pfizer. Any investigators who later join the study will do the same before performing study related duties. For studies of applicable duration, the investigator and sub investigators will complete Pfizer GCP Training or equivalent every 3 years during the term of the study, or more often if there are significant changes to the ICH GCP guidelines or course materials.

2. Study Intervention

No participants or third-party payers will be charged for study intervention.

3. Urgent Safety Measures

In addition, the investigator will inform Pfizer immediately of any urgent safety measures taken by the investigator to protect the study participants against any immediate hazard, and of any serious breaches of this protocol or of ICH GCP that the investigator becomes aware of.

4. Termination Rights

Pfizer retains the right to discontinue development of PF-04449913 at any time.

The investigator agrees to abide by the ethical principles set forth in the World Health Organization’s *Guiding Principles for Human Cell, Tissue and Organ Transplantation* (WHA63.22) (<http://www.who.int/transplantation/en/>) with regard to the study.

10.9. Appendix 9: Strong and Moderate CYP3A4/5 Inducers

Strong CYP3A4/5 Inducers	
Inducer	Therapeutic Class
Rifampin	Antibiotics
Ivosidenib	Antineoplastics
Rifapentine	Antibiotics
Avasimibe	Antilipidemics
Phenytoin	Anticonvulsants
Carbamazepine	Anticonvulsants
Phenobarbital	Anticonvulsants
Enzalutamide	Antiandrogens
Apalutamide	Antiandrogens
St. John's Wort	Herbal Medications
Mitotane	Antineoplastics
Lumacaftor	Cystic Fibrosis Treatments
Moderate CYP3A4/5 Inducers	
Inducer	Therapeutic Class
Semagacestat	Alzheimer's Treatments
Bosentan	Endothelin Receptor Antagonist
Genistein	Food Product
Thioridazine	Antipsychotics
Nafcillin	Antibiotics
Daclatasvir and asunaprevir and beclabuvir	Antivirals
Lopinavir	Protease Inhibitor
Tipranavir and ritonavir	Protease Inhibitors
Modafinil	Psychostimulant
Efavirenz	NNRTI
Etravirine	NNRTI
Lersivirine	NNRTI
Talviraline	NNRTI
PF-06282999	Myeloperoxidase Inactivators
Telotristat ethyl	Antidiarrheals
Lesinurad	Antigout and Uricosuric Agents
Dabrafenib	Kinase Inhibitors
Cenobamate	Anticonvulsant
Rifabutin	Antibiotic
Lorlatinib	Kinase Inhibitor
Elagolix	GnRH Antagonist

Source: University of Washington Drug Interaction Database. "Copyright University of Washington 2005-2018, UW Metabolism and Transport Drug Interaction Database, Oct2020".

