6.5.1. Restricted or Prohibited Concomitant Medications

The following medications are not allowed during the active study treatment period:

- Agents used to treat AML or MDS;
- Investigational agents; This exclusion **does not apply** to any COVID-19 vaccine.
- CYP3A4/5 Strong Inducers: A drug-drug interaction study in healthy participants with the strong CYP3A4 inducer, rifampin, resulted in a 70% decrease in plasma exposures (AUC_{inf}) and a 35% decrease in peak plasma concentration (C_{max}) of a single 100 mg oral dose of glasdegib. Therefore, coadministration of glasdegib and strong CYP3A4/5 inducers is not permitted. A comprehensive list of strong CYP3A4/5 inducers is provided in [Appendix 9](#). The Sponsor study team should be contacted if there is uncertainty whether a concomitant medication is contraindicated.
- CYP3A4/5 Moderate Inducers ([Appendix 9](#)): Avoid concomitant use of glasdegib with moderate CYP3A4 inducers. If use cannot be avoided, double the glasdegib

PFIZER CONFIDENTIAL

dose, as tolerated. After the moderate CYP3A4 inducer has been discontinued for 7 days, resume glasdegib dose taken prior to initiating the moderate CYP3A4 inducer.

The following medications have use restrictions during the active study treatment period:

- **CYP3A4/5 Inhibitors:** In a healthy volunteer study, ketoconazole, a potent CYP3A4/5 inhibitor, produced a 2.4 fold increase in plasma exposure and a 1.4 fold increase in peak plasma concentration of glasdegib. Therefore, a potential exists for drug-drug interactions with CYP3A4/5 inhibitors, and coadministration of glasdegib in combination with strong/ moderate CYP3A4/5 inhibitors is not recommended. Selection of concomitant medication with no or minimal CYP3A4/5 inhibition potential is recommended. Strong/moderate CYP3A4/5 inhibitors ([Appendix 10](#) or [Appendix 11](#)) should be used with caution and only if considered medically necessary. If a moderate/strong CYP3A4/5 inhibitor is to be initiated in addition to glasdegib, the guidance provided in [Appendix 6](#).

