- **Drugs with a known risk of TdP:** Glasdegib has been shown to have the potential to prolong the QTc interval in preclinical studies. In the first in participant study as single agent, Grade 3 QTcF prolongation was observed at the highest doses tested (400 mg and 600 mg). While the glasdegib dose evaluated in this study is 100 mg, the concomitant administration of glasdegib and drugs with a known risk of Tdp should be avoided whenever possible. A list of such drugs is provided in [Appendix 12](#). Use of these drugs is not recommended unless there are no alternatives. If a TdP drug is to be initiated in addition to glasdegib the guidance provided in [Section 6.6.1](#) dose modifications for QT prolongation per [Table 3](#) must be followed.
- QT prolonging medications (without a risk of TdP) should be avoided whenever possible.
- Concomitant administration of multiple moderate/strong CYP3A4/5 inhibitors, TdP drugs, and/or QT prolonging medications (without a risk of TdP) is not recommended.

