10.10. Appendix 10: Strong CYP3A4/5 Inhibitors

Strong CYP3A4/5 Inhibitors	
Inhibitor	Therapeutic Class
Ketoconazole	Antifungal
Itraconazole	Antifungal
Voriconazole	Antifungal
Posaconazole	Antifungal
Troleandomycin	Antibiotics
Clarithromycin	Antibiotics
Telithromycin	Antibiotics
Mibepradil	Calcium Channel Blocker
Conivaptan	Diuretics
Nefazodone	Antidepressants
Cobicistat	--
Indinavir/Ritonavir	Protease Inhibitors
Tipranavir/Ritonavir	Protease Inhibitors
Ritonavir	Protease Inhibitors
Indinavir	Protease Inhibitors
Nelfinavir	Protease Inhibitors
Saquinavir	Protease Inhibitors
Saquinavir/Ritonavir	Protease Inhibitors
Lopinavir/Ritonavir	Protease Inhibitors
Telaprevir	Antivirals
Boceprevir	Antivirals
Danoprevir/Ritonavir	Antivirals
VIEKIRA PAK	Antivirals
Elvitegravir/Ritonavir	Treatment of AIDS
LCL161	Cancer treatment
Idelalisib	Kinase Inhibitors
Ribociclib	Kinase Inhibitors
Grapefruit Juice DS	Food Products
Mifepristone	Antiprogestins
Ceritinib	Kinase Inhibitor
Tucatinib	Kinase Inhibitor

Source: University of Washington Drug Interaction Database. "Copyright University of Washington 2005 2018. UW Metabolism and Transport Drug Interaction Database, October 2020."

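### The rule to double glasdegib with an unavoidable moderate CYP3A4 inducer makes no exception for drugs the protocol also lists as strong inhibitors or known torsade risks

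*Protocol*

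**What the plan says.** Section 6.5.1 of the protocol handles three groups of drugs.

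- **Moderate CYP3A4/5 inducers (Appendix 9).** These stand under the heading for medications barred during active treatment. Their own bullet then softens this. They are to be avoided, but "If use cannot be avoided, double the glasdegib" "dose, as tolerated. After the moderate CYP3A4 inducer has been discontinued for 7 days" the previous dose is resumed.
- **Strong and moderate CYP3A4/5 inhibitors (Appendices 10 and 11).** These stand under the heading for medications with use restrictions. They are not recommended and "should be used with caution and only if considered medically necessary". The bullet gives no glasdegib dose and points to Appendix 6.
- **Drugs with a known risk of torsade de pointes (Appendix 12).** These are to be avoided where possible and used only if there is no alternative, with the QT rules of Table 3 then applying.

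Appendix 9 lists "Tipranavir and ritonavir", lopinavir and thioridazine as moderate inducers. Appendix 10 lists "Tipranavir/Ritonavir" and lopinavir with ritonavir as strong inhibitors. Appendix 12 lists thioridazine.

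Section 6.6.1 explains that inhibitors and torsade drugs are discouraged because the interaction may prolong QTc. It also bars re-escalation after a dose reduction.

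**The concern.** The doubling rule assumes that a listed moderate inducer only lowers glasdegib exposure. That assumption is not safe for a drug that the same protocol lists as a strong inhibitor of glasdegib's metabolism, or as a torsade risk in its own right. A site that looks the drug up in Appendix 9 and follows Section 6.5.1 to the letter would double a QT-prolonging agent in the setting where Section 6.6.1 urges care.

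Safety is the only objective of Amendment 6, and Grade 3 or 4 mQTcF prolongation is its protocol-specified SAE (Section 8.3.11). ECGs are now done at each site's standard of care (Section 1.3), so how soon a problem is seen depends on local practice.

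**Working it through.** **Step 1. Overlap between the lists.** Inputs: Appendix 9 (12 strong and 21 moderate inducers), Appendix 10 (31 strong inhibitors), Appendix 11 (34 moderate inhibitors) and Appendix 12 (known torsade drugs). Only the moderate inducers carry the doubling rule; strong inducers are not permitted at all.

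| Moderate inducers in Appendix 9 (21) compared with | Overlap |
|---|---|
| Appendix 10, same entry | 1: tipranavir with ritonavir |
| Appendix 10, as part of a combination | 1 more: lopinavir, listed there with ritonavir |
| Appendix 11 | 0 |
| Appendix 12 | 1: thioridazine |

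Three of the 21 moderate-inducer entries are affected (1 + 1 + 1 = 3). The lopinavir entries are not the same product. They meet only when lopinavir is given with ritonavir.

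**Step 2. Which rule applies when use cannot be avoided.**

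| Label | Glasdegib instruction |
|---|---|
| Moderate inducer | Double, as tolerated |
| Strong inhibitor | None; caution and medical necessity only |
| Known torsade drug | None at the start; Table 3 if QTcF is prolonged |

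The only active dose instruction is to double, and nothing limits it for a drug with a second label.

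**Step 3. Does other text limit it?**

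- Appendix 6, to which both the inhibitor bullet and Section 6.6.1 point, lists ECG findings that may or do count as AEs or SAEs. It has no dose rule.
- The sponsor-contact sentence in the strong-inducer bullet reads "The Sponsor study team should be contacted if there is uncertainty whether a concomitant medication is contraindicated". It concerns whether a drug may be used, not the glasdegib dose.
- Section 6.6.1 requires Medical Monitor agreement for departures from the dose modifications. A site that doubles under Section 6.5.1 is following the protocol, so this check need not be triggered.
- Table 3 acts once prolongation has been found.
- Sections 6.6.1 and 8 set general duties: awareness of QTcF potential, and discussion of safety issues with the sponsor.

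**Step 4. Size of the dose.** Inputs: Table 1 levels of 100, 75, 50 and 25 mg; Section 6.5.1, which says "While the glasdegib dose evaluated in this study is 100 mg" and reports Grade 3 QTcF prolongation at 400 mg and 600 mg in the first single-agent patient study.

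- 2 × 100 = 200 mg.
- 200 / 100 = 2.0 times the highest Table 1 level.
- 200 / 400 = 0.5 of the lower dose with reported Grade 3 prolongation.

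For a participant already reduced to 75 mg, doubling would give 2 × 75 = 150 mg, if it is allowed. The protocol does not say whether the bar on re-escalation overrides this temporary doubling.

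**Step 5. Reach.** The maximum is 34 + 3 = 37 participants (Section 4.1), some on azacitidine without glasdegib. Nothing in the documents suggests that any of them takes these drugs.

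**The case against.** The strongest reply is that this is a gap rather than a contradiction. The inhibitor rule names no dose, so a site can obey both rules: avoid the drug, use it only if necessary, and adjust as tolerated. A drug can properly be on both an inducer and an inhibitor list, and doubling may be right if induction prevails. Moderate inducers also stand under the barred heading, the two bullets are close together, Appendix 10 directly follows Appendix 9 and lists ritonavir alone as well, and the sponsor-contact sentence is worded to cover any concomitant medication. Much of this stands. It makes unthinking doubling less likely, but it puts no limit on the one dose instruction given.

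A reader might infer three stronger things that the documents do not support.

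- *That the two rules prescribe opposed doses.* They do not; only one prescribes a dose.
- *That doubling would bring exposure into the range where Grade 3 prolongation was seen.* Section 6.5.1 gives a 2.4-fold exposure increase with ketoconazole, and 2 × 2.4 = 4.8, equivalent to 480 mg at a 100 mg dose. That assumes inhibition equal to ketoconazole, no induction, and exposure proportional to dose. None of these is established here for tipranavir with ritonavir.
- *That one of the listings is an error.* Nothing shows this.

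It can also be said that the remedy is only another sponsor contact and sets no dose. That is true. What it changes is the default: the dose is not doubled until someone has considered both labels.

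**Conclusion.** The point holds as an unqualified doubling rule. Three of 21 moderate-inducer entries carry a second label, as a strong inhibitor or a known torsade drug, and the protocol does not hold back doubling for them. At 100 mg the written rule gives 200 mg, twice the highest Table 1 level. Thioridazine is the plainest case, because its listed QT hazard does not depend on an unknown net effect on CYP3A4. For tipranavir or lopinavir with ritonavir, whether doubling is harmful or appropriate turns on a net effect that the documents do not give, so harm is possible but not shown.

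A reader might take the re-escalation bar to protect participants already on 75 mg or less. The text does not settle that either way.

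The practical weight is low. At most 37 participants could be affected, probably none, and no endpoint, analysis set or summary changes. This is a minor point worth correcting because the correction is so cheap. The list matches were made on the text of the appendices as they stand.

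**What to change.** Keep all current listings unless the sponsor finds one to be wrong. Add one sentence to the moderate-inducer bullet of Section 6.5.1:

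*Do not double glasdegib for any drug that is also listed, alone or as part of the combination being given, in Appendix 10, 11 or 12 without prior sponsor agreement.*

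The reference to combinations brings in lopinavir with ritonavir, and Appendix 12 brings in thioridazine. Appendix 11 has no overlap today; naming it keeps the rule valid if the lists are updated. The sentence does not settle the re-escalation question, which the sponsor could answer in the same edit.

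Cost: a rare extra sponsor contact, and possibly a short period of underexposure to glasdegib if the drug proves to be a net inducer. No added procedures, participants or analyses.

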10.10. Appendix 10: Strong CYP3A4/5 Inhibitors

Strong CYP3A4/5 Inhibitors	
Inhibitor	Therapeutic Class
Ketoconazole	Antifungal
Itraconazole	Antifungal
Voriconazole	Antifungal
Posaconazole	Antifungal
Troleandomycin	Antibiotics
Clarithromycin	Antibiotics
Telithromycin	Antibiotics
Mibepradil	Calcium Channel Blocker
Conivaptan	Diuretics
Nefazodone	Antidepressants
Cobicistat	--
Indinavir/Ritonavir	Protease Inhibitors
Tipranavir/Ritonavir	Protease Inhibitors
Ritonavir	Protease Inhibitors
Indinavir	Protease Inhibitors
Nelfinavir	Protease Inhibitors
Saquinavir	Protease Inhibitors
Saquinavir/Ritonavir	Protease Inhibitors
Lopinavir/Ritonavir	Protease Inhibitors
Telaprevir	Antivirals
Boceprevir	Antivirals
Danoprevir/Ritonavir	Antivirals
VIEKIRA PAK	Antivirals
Elvitegravir/Ritonavir	Treatment of AIDS
LCL161	Cancer treatment
Idelalisib	Kinase Inhibitors
Ribociclib	Kinase Inhibitors
Grapefruit Juice DS	Food Products
Mifepristone	Antiprogestins
Ceritinib	Kinase Inhibitor
Tucatinib	Kinase Inhibitor

Source: University of Washington Drug Interaction Database. "Copyright University of Washington 2005 2018. UW Metabolism and Transport Drug Interaction Database, October 2020."

10.11. Appendix 11: Moderate CYP3A4/5 Inhibitors

Moderate CYP3A4/5 Inhibitors	
Inhibitor	Therapeutic Class
Fluconazole	Antifungals
Ravuconazole	Antifungals
Isavuconazole	Antifungals
Erythromycin	Antibiotics
Ciprofloxacin	Antibiotics
Diltiazem	Calcium Channel Blockers
Verapamil	Calcium Channel Blockers
Dronedarone	Antiarrhythmics
Aprepitant	Antiemetics
Casopitant	Antiemetics
Netupitant	Antiemetics
Tofisopam	Benzodiazepines
Cyclosporine	Immunosuppressant
Schisandra sphenanthera	Herbal Medication
ACT-178882	Renin Inhibitor
Cimetidine	H2 Receptor Antagonist
FK1706	Central Nervous System Agent
Faldaprevir	Antivirals
Letermovir	Antivirals
Crizotinib	Kinase Inhibitor
Nilotinib	Kinase Inhibitor
Atazanivir/Ritonavir	Protease Inhibitor
Darunavir	Protease Inhibitor
Darunavir/Ritonavir	Protease Inhibitor
Atazanavir	Protease Inhibitor
Fedratinib	Kinase Inhibitor
Imatinib	Antineoplastic agent
GSK2647544	Alzheimer's Disease & Dementia Treatments
Grapefruit Juice	Food Products
Duvelisib	Kinase Inhibitor
ACT-539313	Hypnotic - Sedative
Lefamulin	Antibiotic
Istradefylline	Other Antiparkinsonians
Voxelotor	Hemoglobin S Polymerization Inhibitor

Source: University of Washington Drug Interaction Database. "Copyright University of Washington 2005-2018. UW Metabolism and Transport Drug Interaction Database, October 2020."

10.12. Appendix 12: List of Drugs with Known Risk of Torsade de Pointes

The following drugs are known to have the risk of Torsade de Pointes due to QTc prolongation and their current use in combination with glasdegib is not recommended. If any of these drugs are considered to be medically necessary, then they should be used with caution in combination with glasdegib.

Generic Name	Drug Class	Therapeutic Use	Route
Aclarubicin (Only on Non US Market)	Anti-cancer	Cancer	injection
Amiodarone	Anti-arrhythmic	Abnormal heart rhythm	oral, injection
Anagrelide	Phosphodiesterase 3 inhibitor	Thrombocythemia	oral
Arsenic trioxide	Anti-cancer	Leukemia	injection
Astemizole (Removed from Market)	Antihistamine	Allergic rhinitis	oral
Azithromycin	Antibiotic	Bacterial infection	oral, injection
Bepridil (Removed from Market)	Anti-anginal	Heart pain	oral
Chloroquine	Anti-malarial	Malaria infection	oral
Chlorpromazine	Anti-psychotic/Anti-emetic	Schizophrenia, nausea, many others	oral, injection, suppository
Cilostazol	Phosphodiesterase 3 inhibitor	Intermittent claudication	oral
Ciprofloxacin	Antibiotic	Bacterial Infection	oral, injection
Cisapride (Removed from market)	GI stimulant	Increase GI motility	oral
Citalopram	Anti-depressant, SSRI	Depression	oral
Clarithromycin	Antibiotic	Bacterial infection	oral, inhaled
Cocaine	Local anesthetic	Anesthesia (topical)	oral, nasal
Disopyramide	Anti-arrhythmic	Abnormal heart rhythm	oral, injection
Dofetilide	Anti-arrhythmic	Abnormal heart rhythm	oral

Generic Name	Drug Class	Therapeutic Use	Route
Domperidone (Only on Non US market)	Anti-emetic	Nausea, vomiting	oral, injection, suppository
Donepezil	Cholinesterase inhibitor	Dementia (Alzheimer's Disease)	oral
Dronedarone	Anti-arrhythmic	Atrial Fibrillation	oral
Droperidol	Anti-psychotic/Anti-emetic	Anesthesia adjunct, nausea	injection
Erythromycin	Antibiotic	Bacterial infection; increase GI motility	oral, injection
Escitalopram	Anti-depressant, SSRI	Major depression/ Anxiety disorders	oral
Flecainide	Anti-arrhythmic	Abnormal heart rhythm	oral
Fluconazole	Anti-fungal	Fungal infection	oral, injection
Gatifloxacin (Removed from market)	Antibiotic	Bacterial infection	oral, injection
Grepafloxacin (Removed from market)	Antibiotic	Bacterial infection	oral
Halofantrine (Only on Non US market)	Anti-malarial	Malaria infection	oral
Haloperidol	Anti-psychotic	Schizophrenia, agitation	oral, injection
Hydroquinidine	Anti-arrhythmic	Arrhythmia	oral
Ibogaine (Only on Non US market)	Psychedelic	Narcotic addiction, unproven	oral
Ibutilide	Anti-arrhythmic	Abnormal heart rhythm	injection
Levofloxacin	Antibiotic	Bacterial infection	oral, injection
Levomepromazine (methotrimeprazine) (Only on Non US Market)	Anti-psychotic	Schizophrenia	oral, injection
Levomethadyl acetate (Removed from market)	Opiate	Narcotic dependence	oral
Levosulpiride (Only on Non US market)	Anti-psychotic	Schizophrenia	oral, injection

Generic Name	Drug Class	Therapeutic Use	Route
Mesoridazine (Removed from market)	Anti-psychotic	Schizophrenia	oral
Methadone	Opiate	Pain control, narcotic dependence	oral, injection
Meglumine Antimonite	Anti-parasitic	Leishmaniasis	injection
Moxifloxacin	Antibiotic	Bacterial infection	oral, injection
Nifekalant	Anti-arrhythmic	Arrhythmia	oral
Ondansetron	Anti-emetic	Nausea, vomiting	oral, injection
Oxaliplatin	Anti-cancer	Cancer	injection
Papaverine HCl (Intra-coronary)	Vasodilator, Coronary	Diagnostic adjunct	injection
Pentamidine	Anti-fungal	Pneumocystis pneumonia	injection, inhaled
Pimozide	Anti-psychotic	Tourette's tics	oral
Probucol (Removed from market)	Antilipemic	Hypercholesterolemia	oral
Procainamide	Anti-arrhythmic	Abnormal heart rhythm	injection
Propofol	Anesthetic, general	Anesthesia	injection
Quinidine	Anti-arrhythmic	Abnormal heart rhythm	oral, injection
Roxithromycin (Only on Non US market)	Antibiotic	Bacterial infection	oral
Sevoflurane	Anesthetic, general	Anesthesia	inhaled
Sertnidole	Anti-psychotic	Schizophrenia, anxiety	oral
Sotalol	Anti-arrhythmic	Abnormal heart rhythm	oral
Sparfloxacin (Removed from market)	Antibiotic	Bacterial infection	oral
Sulpiride (Only on Non US market)	Anti-psychotic, atypical	Schizophrenia	oral, inhaled
Sultopride (Only on Non US market)	Anti-psychotic, atypical	Schizophrenia	oral, injection
Terfenadine (Removed from market)	Antihistamine	Allergic rhinitis	oral

Generic Name	Drug Class	Therapeutic Use	Route
Terlipressin (Only on Non US market)	Vasoconstrictor	Septic shock	injection
Terodiline (Only on Non US market)	Muscle relaxant	Bladder spasm	oral
Thioridazine	Anti-psychotic	Schizophrenia	oral
Vandetanib	Anti-cancer	Thyroid cancer	oral

Source: CredibleMeds.org (<http://crediblemeds.org/healthcare providers/drug list/?rf>All>). TdP risk category filtered on Drugs with known TdP risk. December 2020.

10.13. Appendix 13: Protocol Amendment History

The protocol Amendment Summary of Changes Table for the current amendment is located directly before the TOC. The protocol amendment summary of changes tables for past amendment(s) can be found below:

Document History		
Document	Version Date	Summary and Rationale for Changes
Amendment 5	12 April 2019	
Note that 2 tables have been removed from the introduction section, resulting in updated table numbers.
 
Schedule of Activities:
 
Tables 1 and 3, Footnote 1: clarify that assessments performed as standard of care within 28 days of randomization do not need to be repeated to be used for screening.
 
Tables 1 and 3, Footnote 4: clarified that Response Assessment includes assessment of EMD (eg, disease in CSF).
 
Table 1, Footnotes 6 and 7: clarified that weekly hematology and chemistry tests must continue weekly until the next phase of study/treatment begins.
 
Table 1, Footnote 14 and Table 3, Footnote 13: Morning dosing of therapy is preferred but not mandatory, rationale for change added to Section 5.5.1.1.
 
Tables 1 and 3, Deleted individual rows for each Patient Reported Outcome survey since they are administered together and are outlined in footnote and Section 7.4.
 
Table 1, Footnote 32 and Table 3, Footnote 36: added “if able” to the PRO collection during HSCT period.
 
Table 3 and Section 5.5.1.3: Participants enrolled in the Non Intensive study may undergo HSCT per local standard of care and at the Investigator’s discretion.
 
Table 1, Footnotes 26, 27, 38 and Table 3, Footnotes 24, 25, 31: Updated with text related to China samples.

Document History		
Document	Version Date	Summary and Rationale for Changes
		
Table 1, Footnote 19, Table 3, Footnote 16 and Section 7.2.3: Bone marrow assessments within 3 weeks of growth factor administration are evaluable and do not need to be repeated. Original text that these BM assessments would not be considered evaluable has been deleted.
 
Introduction: Background (Section 1.2) and Rationale sections have been separated and updated to reflect current data and IB.
 
Removed Nonclinical Toxicology text (Section 1.2.3).
 
Clinical Development (Section 1.2.4): Removed Table 5 and Table 6. Safety and Efficacy sections removed and new section inserted describing Glasdegib Clinical Pharmacology. Updates to relevant clinical studies with glasdegib made to provide relevant background. Data from thorough QTc study included.
 
Section 4.2, Inclusion/Exclusion:
 
Inclusion #1: Clarified that participants with FLT3+ AML not receiving and not intended to receive a FLT3 inhibitor during study participation are allowed per regulatory agreement.
 
Inclusion #5: Removed ATRA since it is meant to treat APL and removed anageride. Text added, continuation or resumption of hydroxyurea or leukapheresis after described time period must be approved by the Sponsor.
 
Exclusion #1: Clarified that APL is associated with t(15;17).
 
Exclusion #2: Clarified that the mutation must be known.
 
Exclusion #4: QTc exclusion does not apply to participants with cardiac pacemaker.
 
Exclusion #14: Removed local radiation as an excluded treatment modality during the screening period.

Document History		
Document	Version Date	Summary and Rationale for Changes
		
Section 4.3: Text added defining Screen Failures as participants who consent to participate in the clinical study but are not subsequently randomized. Added data collection required for Screen Failure participants.
 
Section 4.4.1: Text updated to require one method of birth control, consistent with sponsor requirements. Language added to clarify Investigator responsibility for reproductive capability assessment.
 
Table 6: Updated to include abstinence.
 
Section 4.4.2: Added to provide postmenopausal definition.
 
Section 5.2 Breaking the Blind: Text now reflects that CRF does not collect Break blind data, but that this will be documented within the source. Additionally, participants may not continue on study treatment once an investigator breaks the blind for that participant.
 
Section 5.5.1.2: Clarification text added regarding the timing and terms of bone marrow assessments.
 
Section 5.5.2: Adverse events and concomitant medications will not be collected during long-term follow-up.
 
Table 10 Glasdegib/placebo Dose Modifications for mean QTcF Prolongation: updated in alignment with the USPI. Also added comment that mQTcF dose mods do not apply to participants with cardiac pacemakers.
 
Figure 2: Updated for clarity and to align terms with CRF fields.
 
Figure 3: Updated with addition of option for HSCT.
 
Section 5.8.1: Removed requirement of discussion with Medical Monitor for the concomitant use of CYP3A4 inhibitors/inhibitors.
 
Section 5.8.2.2: Removed text requiring a repeat BM assessment if done within 3 weeks from last

Document History		
Document	Version Date	Summary and Rationale for Changes
		
dose of growth factor. Growth factors may be given per local standard of care and local label.
 
Section 6.4, Table 1, Footnote 31 and Table 3, Footnote 29: Text added regarding the use of public records for long term survival follow-up as allowed by local law.
 
Section 7.2.1: Additional text describing the AML response assessment added for clarity.
 
Section 7.2.2: Text added allowing post baseline genetic assessments to be limited to abnormalities noted at baseline and molecular assessments to follow standard of care.
 
CCI [REDACTED]
 
Add Section 7.3.2: Biomarker Assessments: Updated to reflect current biomarker plans.
 
Section 7.4: Updates to account for hospitalized participant schedules, participants with visual problems, and clarification that for patients hospitalized or with a timepoint falling on a weekend or holiday, PRO questionnaires may be performed on the next business day.
 
Section 7.1.4: Re-screening is allowed.
 
Section 9:
 
9.1: clarified percentage of patients censored for OS used in the sample size determination.
 
9.2: clarified all analyses of intensive and nonintensive chemotherapy participants will be conducted separately and independently of each other.
 
9.3.1 : added region (rest of world versus China) as a stratification factor to the primary and secondary analyses for intensive patients due to potentially different rates of stem cell transplantation.
 
9.3.2 : clarified all secondary PRO and efficacy endpoints will be based on the full analysis set unless stated otherwise; clarified method for calculating confidence intervals for binary efficacy

Document History		
Document	Version Date	Summary and Rationale for Changes
		
endpoints; removed Kaplan-Meier analysis for time to response as analysis is for responders only; clarified censoring for those without event-free survival events; clarified which event-free survival methods are for responders only.
 
9.4: clarified transfusion conversion rate is analyzed in the safety analysis set.
 
9.5.1: clarified safety analyses are analyzed in both intensive and non-intensive studies.
 
9.7: clarified DMC will convene at least once yearly per DMC charter.
 
Clarified throughout document that restarting glasdegib/placebo Post HSCT requires no ongoing \geq Grade 2 GVHD.
 
Section 14: Added text regarding options for Non-Intensive participants to continue treatment at study end.
 
Appendix 1: Added abbreviation for HGRAC.
 
Appendix 4: Updates for clarity and readability.
 
Appendices 5, 6, 7, 8 and references updated.
 
General spelling, grammar, repetitions and formatting corrected.

Amendment 4	02 July 2018	
Amendment 4 changes will be applicable to participants enrolling in Germany.
 
German ethics committee requested collection of unrelated SAEs during the HSCT period. This edit was made in Section 8.1.
 
Section 9.5.1: deleted text impacted by update to Section 8.1.

Amendment 3	01 March 2018	
All changes were made prior to start of the study in response to regulatory requests except where indicated. Other minor changes were added for clarity.
 
Added BRIGHT AML1019 study logo to cover page.

Document History		
Document	Version Date	Summary and Rationale for Changes

Endpoints: clarified response definition by defining CR_i or better to include CR (including CR_{MRD-negative}) or CR_i for intensive chemotherapy participants, and CR (including CR_{MRD-negative}), CR_h, or CR_i for non-intensive chemotherapy participants. CR_h or better is only defined for non-intensive chemotherapy participants as CR (including CR_{MRD-negative}) or CR_h. Also updated Section 9.3 (and subsections) and Appendix 4 with these definitions.
 
Schedule of Activities:
 
Clarified that bone marrow assessments for study assessments other than disease classification must be done after informed consent signed in footnotes, as specified in the Protocol Administrative Change Letter, dated 20 Dec 2017.Added whole blood collection for immunophenotyping and molecular profiling on Day 1, prior to dosing study drug to provide a baseline sample to compare to future samples for MRD assessment.Removed whole blood collection for pharmacogenomic analysis from intensive and non-intensive chemotherapy studies because pharmacogenomic analysis of drug metabolizing enzymes and transporters was no longer a priority for this study as it was unlikely to provide valuable information that would inform either safety or efficacy. Also removed Section in protocol defining this analysis.Added additional times when bone marrow samples must be collected post consolidation for the Intensive Study so MRD status may be confirmed in a timely manner.Table 3: blood chemistry deleted from follow-up visits; added in error.		

Document History		
Document	Version Date	Summary and Rationale for Changes
		
Section 1.2.3: Edited text for glasdegib nonclinical toxicity to align with updated data.
 
Inclusion criterion #5: specified anti-cancer agents for clarity in response to regulatory request.
 
Exclusion criteria #7: removed right bundle branch blocks as this is common and it should not be excluded.
 
Section 4.3.1: Added a requirement for a backup contraception method in response to regulatory request.
 
Section 5.4.1.3: removed subcutaneous route for cytarabine since this will not be an option.
 
Removed term allogeneic because either autologous or allogeneic HSCT is allowed during the Intensive Chemotherapy Study per regulatory feedback.
 
Section 5.8.1: re-organized CYP3A4/5 inducers so bullet appears under proper heading.
 
Table 11 now specifies that glasdegib/placebo should be permanently discontinued for all cases of confirmed DILI/Hy's Law and potential cases require glasdegib/placebo dose interruption and potential restarting. Added in response to regulatory request.
 
Table 14 now includes required bicarbonate testing to determine dose reductions per azacitidine label, per regulatory request. Also clarified indication for U/A with microscopic evaluation and 24-hour urine protein.
 
Sections 7.1.7: removed additional QTc monitoring requirements if a moderate/strong CYP3A4/5 inhibitor or TdP drug administered during study since additional monitoring was not required.
 
Section 9.3: Changes in the PRO section were made to improve clarity regarding planned analyses per regulatory request. Other changes

Document History		
Document	Version Date	Summary and Rationale for Changes
		
clarified method by which response will be analyzed.
 
Removed section specifying end of trial in a member state because LSLV will be considered the end of trial in all participating countries.
 
Removed due to regulatory request.
 
Appendix 16 added per country specific requirement in France.
 
General spelling, grammar, and consistency issues corrected throughout the protocol.

Amendment 2	15 November 2017	
All changes were made prior to start of the study in response to FDA request except where indicated. Other minor changes were added for clarity.
 
Secondary endpoints updated:
 
• CR/CRh was added to duration of response assessment to match statistical analysis section.• CR/CRh was added to time to response assessment to match statistical analysis section.• Schedule of Activities (Intensive study): Pregnancy testing added for Day 1 of each Consolidation Cycle with single agent cytarabine and Day 1 of each cycle where single agent glasdegib/placebo administered to ensure appropriate safety monitoring.• Schedule of Activities (Intensive and Nonintensive studies): Immunophenotyping was removed because it is not required for any study analysis. Immunophenotyping was also removed from Sections 7.1 and 7.2.2 for consistency. 
X's added to tables so tables now match footnotes indicating specified instances AEs and SAEs may be collected during the follow-up period.
 
Table 2 and Table 4 now provide time windows for assessments allowing sites flexibility in obtaining assessments without jeopardizing data.

Document History		
Document	Version Date	Summary and Rationale for Changes
		
Other minor footnote clarifications to ensure consistency with tables.
 
Inclusion Criterion #4: removed bullet indicating that the criterion does not apply to participants with bundle branch blocks and is otherwise asymptomatic. This conflicted with an exclusion criterion and was confusing.
 
Exclusion Criterion #4: specified that a participant could not participate in other clinical studies involving other investigational drugs to clarify that this did not apply to glasdegib in this study.
 
Section 5.4.1.2: Reduced the text describing the azacitidine supply to match information supplied for other chemotherapy drugs in this study. Edits added for clarity, instructing sites to follow local regulations.
 
Section 5.5.5 updated per FDA request to provide more information regarding glasdegib/placebo dose modifications.
 
• Corrected typographical error in Section 5.5.1 indicating that glasdegib or placebo does not need to be delayed or dose reduced for hematologic, study treatment related toxicity.• Specified dose escalations will not be allowed following glasdegib/placebo dose reductions.• Added Section 5.5.2 for dosing interruptions for glasdegib/placebo non-hematological toxicities.• Section 5.8.1: corrected a typographical error, removing word permitted. 
Section 7.1.3: Added text specifying that assessment of acute GVHD will be graded by standard criteria based on the Consensus conference on acute GVHD grading and assessment of chronic GVHD will be assessed based on the NIH criteria with associated

Document History		
Document	Version Date	Summary and Rationale for Changes
		
references. Grading and Staging for acute GVHD is summarized in Appendix 15.
 
• Section 7.1.4: Clarified that laboratory tests only need to be obtained during screening, and there is no need to repeat these tests on Day 1 if performed within 3 days prior to randomization.• Section 7.1.7: specified type of ECGs (supine) for clarity.• Section 7.4.3 updated per FDA request:• Changed PGIS from a 7 point scale to a 4 point scale. The FDA recommended that Pfizer revise the PGIS to 4 response options (eg, absent (no symptoms), mild, moderate, and severe) so patients can easily distinguish severity.• Section 9.2.5: updated for clarity; now specifies Intensive and Nonintensive studies.• Section 9.3.2: updated per FDA request, specifying type of analysis required for fatigue and to correct minor errors. 
This section also includes an update to correct a typographical error: Method 1 sensitivity analysis for EFS must include CRi and Method 4 must not include CRi for the Intensive Study.
 
For the Nonintensive study, Method 2 for the EFS definition now specifies CR or CRi will be evaluated following up to 6 cycles of therapy.
 
Now specifies the Brookmeyer and Crowley method will be used to evaluate EFS for clarity.
 
PK Parameters now specify C_{trough} will be reported for glasdegib metabolites, if relevant. Though there is no activity anticipated for the N-desmethyl metabolite (M3) that is <10% in circulation; possible metabolite measurement is added, if applicable as a conservative approach.

Document History		
Document	Version Date	Summary and Rationale for Changes
		
Appendix 4 updated to match data analysis section for consistency:
 
• Absence of CRh added to SD definition.• Treatment failure definitions added for Intensive and Non-intensive studies.• Appendix 11 updated to address FDA comments: 
PGIS now includes question regarding leukemia symptoms.
 
General spelling, grammar, and consistency issues corrected throughout the protocol.

